## 6. STUDY DRUG ADMINISTRATION

### 6.1. Vosaroxin Formulation

Each vial contains 2,300 mg vosaroxin at a concentration of 10 mg/mL. Each milliliter also contains 45 mg of D-sorbitol to maintain isotonicity. Methanesulfonic acid is added as an aid to solubilize vosaroxin. The sterile nonpyrogenic solution is formulated without preservatives.

### 6.2. Vosaroxin Storage

Vosaroxin vials must be stored as packaged at controlled room temperature, thermostatically maintained from 20°C to 25°C (68°F to 77°F). Do not store above 25°C. Stability data supports variations in prevailing temperature between 15°C and 30°C. Vosaroxin must not be frozen or stored in a refrigerator. When vosaroxin is drawn into a syringe, stability data support a maximum of 2 hours exposure to continuous ambient light. If the syringe containing the product is completely wrapped in foil or other protective covering from ultraviolet and visible light (e.g., amber bag, brown paper bag), this 2-hour stability maximum can be extended up to 24 hours.

### 6.3. Dose Calculation, Preparation, and Administration

#### 6.3.1. Dose Calculation

The administration of study drugs (vosaroxin and cytarabine) requires calculation of body surface area (BSA) using the patient's actual, measured body weight and height. For patients with a BSA > 2.4 m^2, dosing should be calculated using a maximum BSA of 2.4 m^2. The Mosteller formula is recommended to calculate BSA in m^2; however, pharmacy personnel may calculate BSA according to institutional method.

$$\text{Mosteller formula: BSA (m}^2\text{)} = \sqrt{\frac{\text{height (cm)} \times \text{weight (kg)}}{3600}}$$

#### 6.3.2 Preparation and Administration of Vosaroxin

Undiluted vosaroxin should be administered according to these general guidelines:

- Wear gloves and adhere to strict aseptic technique.
- Inspect the vial and confirm it is not cracked or damaged in any way.
- Inspect the solution and confirm it is not discolored and contains no visible particulates.
- Do not infuse vosaroxin in the same IV line (tubing) with sodium chloride solutions or other medications. The product may precipitate in sodium chloride solutions. If no alternative line is available, flushed saline thoroughly with 5% dextrose in water (D5W) before and after administration.

**Suggested Procedure for Preparation**

- Calculate the dose according to physician instructions.
- Attach an appropriate gauge needle to the tip of the sterile plastic syringe that will be used to administer vosaroxin.
- Withdraw the product from the vosaroxin vial into the syringe. Note: a vacuum may result as the product is withdrawn. Avoid or release the vacuum per institutional practice.

Please note that if using a vent needle to aid in drawing investigational product from the vial, the vial should remain upright, and the vent needle should only be inserted into the head space containing air. The needle used to withdraw product should be inserted as far as possible to the bottom of the vial to withdraw the required volume of drug.

If pressurizing a vial, do not use a vent needle. Add the equivalent dose volume of air to the vial headspace in the upright position, invert the vial, insert the syringe needle into the solution, and withdraw the required volume of drug.

- When the syringe contains the entire dose to be administered, cap the syringe and discard the needle.
- Protect the filled, capped syringe from light and whilst in transit to the patient until ready to administer the product.

**Suggested Procedure for Administration**

- A biluminal or triluminal catheter is recommended. Start an IV infusion through one of the lumens using D5W for analogous solution at a slow rate sufficient to keep the vein open.
- Before administration of vosaroxin, increase the D5W infusion rate to approximately 100 mL per hour and continue this rate during the vosaroxin infusion.
- Administer vosaroxin via syringe by assessing and available hub or stopcock.
- Administer vosaroxin as a short infusion within 10 minutes, either manually or using a syringe pump.
- At the end of the infusion, flushed the IV line with D5W per institutional standard.
- If a central catheter or heparin lock is in place, it may be capped according to the sites usual procedures.

Vosaroxin is not known to be a thoracic and/or irritant. If extravasation is observed or suspected, treat according to standard institutional procedures.

## 7. CONCOMITANT MEDICATIONS

Concomitant medications are recommended as prophylaxis for nausea, vomiting, and infections, and Darvon for managing myelosuppression as shown in table 2.

Myelosuppression is expected in patients with AML due to underlying disease, as well as due to chemotherapy (such as vosaroxin and cytarabine), or both. Most patients will have neutropenia, thrombocytopenia, or both at study entry. Myelosuppression may be managed with growth factor support and blood transfusion according to institutional standard of care, American Society of Clinical Oncology (ASCO) Practice Guidelines, and NCCN Practice Guidelines.

Infections secondary to myelosuppression are common in patients with AML, and may be related to underlying disease, chemotherapy, or both. Therefore, the use of prophylactic antibiotics, antifungal agents, and antiviral agents is required. A regimen of levofloxacin (500 mg po daily), fluconazole (400 mg po daily), and valacyclovir (500 mg po q12h) is suggested with substitutions permitted as per institutional formulary. (See Appendix E)

**Table 2. Instructions for the use of concomitant medications and therapies**

Category of use	Medication	Comment on use	Restriction on use
Recommended	Prophylactic antibiotics, antifungal agents, and antiviral agents	Required  (see Appendix E)	None
	Prophylactic antiemetic medications	According to standard of care at individual study site	None
	Mouth Care	Suggested regimen  See Appendix E	See Appendix E
Allowed	Oral allopurinol or rasburicase	At investigator's discretion according to standard of care at individual study site	None
	Leukapheresis		Before induction 1 day 1 only
	Transfusion of red blood cells		None
	Transfusion of platelets		None
	Transfusion of granulocytes		None
	Erythropoietin or darbepoetin		None
	Any other medications for supportive care		Must be necessary for the patient's welfare and expected not to interfere with evaluation of study treatment
Prohibited/Restricted	Hydroxyurea or medications to reduce to blast count	May use transiently for reduction of cells if WBC $\geq$ 50,000	Allowed only $>$ 24hours prior to initiation of protocol defined therapy
	Myeloid growth factors (e.g., sargramostim, filgrastim, pegfilgrastim)	May only use if patient's clinical status declines, and investigator uses as rescue sepsis, etc.	Restricted to neutropenic sepsis, bacteremia or other severe infection
	Investigational products (those not approved for any indication by the FDA or other regulatory authorities)	None	Prohibited until end of protocol defined therapy
	Nonprotocol treatment for acute myeloid leukemia	None	Prohibited until end of protocol defined therapy

## 8. DISCONTINUATION OF TREATMENT

Treatment may be discontinued for a variety of reasons, including patient withdrawal, investigator decision, and reasons specified by the protocol.

### 8.1. Discontinuation Criteria for Individual Patients

#### 8.1.1. Patient Withdrawal

Patients may voluntarily withdraw consent to participate in the clinical study at any time and without giving any reason. Their withdrawal will not jeopardize their relationship with their healthcare providers or affect their future care. Patients may also choose to withdraw from study treatment, but agree to remain in the study for follow up procedures.

#### 8.1.2. Investigator Discontinuation of Patient

The investigator may exercise medical judgment to discontinue study treatment if clinically significant changes in clinical status or laboratory values are noted.

#### 8.1.3. Criteria for Protocol-Defined Required Discontinuation of Treatment

The protocol requires discontinuation of study treatment for the following reasons:

- Maximum allowed treatment completed
- Failure to achieve a CR or CRi after 2 attempts (Induction 1 / 2)
- Disease relapse after a CR or CRi
- Clinically significant neutropenia or thrombocytopenia in the absence of residual leukemia that does not recover to grade  $\leq 2$  within 57 days after the first dose of vosaroxin in any cycle
- Clinically significant treatment related non-hematologic AE in the absence of residual leukemia that does not recover to grade  $\leq 2$  within 8 weeks after the first dose of vosaroxin in any cycle
- Any AE that is unacceptable or intolerable
- Intercurrent illness that prevents the next cycle of treatment
- Pregnancy
- Other non-protocol systemic AML therapy or prohibited medication initiated
- General or specific changes, including protocol violations, rendering the patient unsuitable for further study treatment

#### **8.1.4. Protocol violations and deviations**

Protocol violations are defined as significant departures from protocol required processes or procedures that affect patient safety or benefit potential, or confound assessments of safety or clinical activity. A protocol deviation is a departure from the protocol that does not meet the above criteria. Protocol violations or deviations may be grouped into the following classes:

- Enrollment criteria
- Study activities (missed evaluations or visits)
- Noncompliance with dose or schedule, including dose calculation, administration or discontinuation criteria
- Investigational product handling, including storage and accountability
- Informed consent and ethical issues

The Sponsor is responsible for implementing and maintaining quality assurance and quality control to ensure that studies are conducted according to the protocol, GCP, and all applicable regulatory requirements. A protocol deviation is any noncompliance with the protocol. Noncompliance can be on the part of the study participant, the Investigator, or the study site staff. All protocol deviations are required to be reported to the Sponsor and submitted to the IRB per institutional guidelines. Deviations to the protocol are not permitted except when necessary to eliminate an immediate hazard to study subjects.

### **9. EFFICACY ASSESSMENTS**

#### **9.1. Determination of Overall Survival**

Survival information will be collected for all patients in the study.

#### **9.2. Determination of Response**

The investigator will determine response based on local laboratory findings to guide treatment decisions. Response will be determined based on IWG response criteria as summarized in Table 3.

#### **9.3. Time-to-Event Endpoints**

In addition to OS, time to event endpoints include EFS and LFS.

**TABLE 3. Vosaroxin Response Criteria Based on International Working Group Criteria**

Category	Neutrophils (cells/ $\mu$ l)	Platelets (plt/ $\mu$ l)	Bone marrow blasts (%)	Other requirements
Complete remission (CR)	>1000	$\geq$ 100,000	<5	
 
No Leukemic blasts in peripheral blood.
 
Transfusion independence, except for infection, bleeding, or medical/surgical conditions predisposing to bleeding.
 
No extra medullary disease
 

CR with incomplete count recovery (CRi)	$\leq$ 1000	$\geq$ 100,000	<5	
 
Meets criteria for CR except for neutrophils
 

	>1000	< 100,000	<5	
 
Meets criteria for CR except for platelets
 

Partial Remission (PR)	>1000	$\geq$ 100,000	Decrease of $\geq$ 50% to value between 5% and 25%	
Treatment Failure (TF)	Persistent acute myeloid leukemia in blood or bone marrow, or therapy fails to achieve a remission of any category, or death prior to response assessment			

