  - Recovery marrow assessment to be performed following count recovery (ANC  $> 1000$ , Platelets  $> 100$ ) following the initiation of induction therapy for formal response assessment. Disease assessment will be performed on day 57 ( $\pm 3$  days) for those failing to demonstrate peripheral count recovery, or per the discretion of the investigator.

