## 10. SAFETY ASSESSMENTS

### 10.1. Safety Monitoring

#### 10.1.1. Common Adverse Events Attributed to Vosaroxin

The safety profile of vosaroxin is consistent with the common pharmacologic effects of cytotoxic chemotherapeutic agents. Myelosuppression (including associated fatal infections) and gastrointestinal (GI) toxicity (including nausea, diarrhea, and upper GI mucositis) are known risks associated with vosaroxin treatment. Oral mucositis (stomatitis) was the DLT in patients with hematologic malignancies treated with higher doses of vosaroxin: up to 40 mg/m^2 once weekly for 4 weeks (28-day cycle) or up to 90 mg/m^2 once weekly for 3 weeks (28 day cycle; up to 270 mg/m^2/cycle). In patients treated with vosaroxin, oral mucositis is dose limiting and grade 3 or 4 oral mucositis usually appears within 2 weeks after the first dose.

Per the most recent reference safety information (IB, Version 12), infections and febrile neutropenia were reported at a higher frequencies in patients with hematologic malignancies (39.7% and 36.9 of 648 patients respectively) than in patients with solid tumors (12.3% and 9.2% of 284 respectively). The GI toxicities of stomatitis and diarrhea were also reported at higher frequencies in patients with hematologic malignancies (46.8% and 47.7% respectively) than in

patients with solid tumors (11.3% and 17.3% respectively). For patients with hematologic malignancies who received vosaroxin (N = 648), the most common treatment-related AEs (with at least 20% incidence) include nausea (53.2%), diarrhea (47.7%), stomatitis (46.8%), febrile neutropenia (36.9%), decreased appetite (31.3%), vomiting (30.1%), anemia (29.0%), thrombocytopenia (28.5%), neutropenia (20.1%), and fatigue (21.0%). The only two grade 3 and 4 treatment-related AEs reported in at least 20% of all vosaroxin treated patients (N = 932) are febrile neutropenia (26.4%) and neutropenia (21.5%).

For patients with AML treated with higher doses of vosaroxin, oral mucositis is dose limiting and grade 3 or 4 oral mucositis usually appears within 2 weeks after the first dose. Oral mucositis can be managed with standard supportive care (Appendix E). The incidence of combined grade 3 and 4 nausea and vomiting in vosaroxin studies is low (2.7% and 1.4% respectively).

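### Table 3 classes a count-recovered patient with under 5% blasts who still needs red cells as Treatment Failure, and lets transfusion-supported counts qualify as CR when an exception applies

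*Combined protocol and SAP*

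**What the plan says.** Section 9.2 has the investigator determine response from local laboratory findings, using the IWG criteria as Table 3 summarizes them.

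- **CR:** neutrophils above 1000, platelets at least 100,000, marrow blasts under 5%, no blood blasts, no extramedullary disease, and "Transfusion independence, except for infection, bleeding, or medical/surgical conditions predisposing to bleeding".
- **CRi, first row:** neutrophils at or below 1000 with platelets at least 100,000; "Meets criteria for CR except for neutrophils".
- **CRi, second row:** neutrophils above 1000 with platelets below 100,000; "Meets criteria for CR except for platelets".
- **PR:** marrow blasts between 5% and 25%.
- **Treatment Failure:** includes any patient whose "therapy fails to achieve a remission of any category, or death prior to response assessment".

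Table 2 allows red cell and platelet transfusion and "Transfusion of granulocytes", all without restriction. Section 5.2 defines hematologic recovery by neutrophil and platelet counts alone. The synopsis ties the formal assessment to the same counts: "Recovery marrow assessment to be performed following count recovery". Section 12.4 takes the best response up to the day-84 marrow, for the interim analysis.

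**The concern.** Complete remission is the only primary endpoint, and Table 3 is the rule that produces it. The transfusion clause does two jobs with one phrase. It is meant to show that the marrow is working, yet it is waived for infection and bleeding, which are settings where granulocytes and platelets may be given. It also applies to red cells, although no CRi row provides for a patient whose only shortfall is red-cell need.

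Two things are at stake. The first is the secondary CR/CRi rate and the set of patients followed for 1-year DFS. The second is whether every patient in the primary CR count has recovered their own counts. Because the clause has no time window and response is called locally in an open-label multi-site trial, two sites could also class the same patient differently.

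**Working it through.** **Classification check.** Apply Table 3 literally to a patient with marrow blasts under 5%, no blood blasts and no extramedullary disease.

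| Neutrophils | Platelets | Transfusion | Exception applies? | Class |
|---|---|---|---|---|
| 1500 | 120,000 | none | n/a | CR |
| 1500 | 120,000 | red cells | no | Treatment Failure |
| 1500 | 120,000 | red cells | yes | CR |
| 1500 | 120,000 | platelets or granulocytes | no | Treatment Failure |
| 1500 | 120,000 | platelets or granulocytes | yes | CR |
| 1500 | 60,000 | none | n/a | CRi |
| 1500 | 60,000 | platelets | no | Treatment Failure |
| 800 | 60,000 | none | n/a | Treatment Failure |

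Row 2 is the first route. The patient fails CR on transfusion independence, fails both CRi rows because neither count is low, and fails PR because blasts are under 5%. The residual clause then applies. Row 5 is the second route: the exception removes the bar, and no text requires the counts to be unsupported. The last two rows show that the CRi rows also omit a platelet-supported patient who stays below 100,000 and a patient with both counts low.

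**Size of the first route.** One patient is 1/41 = 2.4 points of the CR/CRi rate. If such a patient belongs in CRi, the CR count does not change.

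**Size of the second route.** First reproduce the plan's figures (section 12.3: stop at 7 or fewer CRs in 17, success at 22 or more in 41, 40% against 60%). With b(n,x,p) the binomial probability:

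- Early termination = P(Bin(17, p) ≤ 7)
- Success = Σ over x = 8 to 17 of b(17, x, p) × P(Bin(24, p) ≥ 22 − x)

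At p = 0.40, early termination is 64.05% (stated 64%), expected sample size is 17 × 0.6405 + 41 × 0.3595 = 25.6 (stated 25.6), and type I error is 4.73% (stated 5%; simulated 4.9%). At p = 0.60, power is 80.1% (stated 80%). The design figures reproduce.

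For the K=4 plan, LR = 1.5^(2r − n). At 22/41 this is 1.5^3 = 3.375, which is weak; at 23/41 it is 1.5^5 = 7.59, which is strong. Success therefore needs 23/41, 28/51 or 33/61, and 19 to 22 of 41 leads to an extension. Exact type I error is 3.45%. The counts in Table 8 give (125 + 32 + 15)/5000 = 3.4%, although the text states 3.7%.

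Now suppose, as an assumption, that supported counts add 1, 2 or 3 points to a true 40% CR rate:

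| Recorded CR rate | Type I error, 22/41 rule | Type I error, K=4 with both extensions |
|---|---|---|
| 40% | 4.73% | 3.45% |
| 41% | 6.17% | 4.70% |
| 42% | 7.91% | 6.29% |
| 43% | 9.99% | 8.25% |

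**The case against.** The strongest reply is that the problem is smaller than it looks, and much of this stands.

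- **The over-count is an input.** The error rates show how sensitive the rule is to any over-count of CR; they are not a forecast. Under K=4, a 1-point shift stays below 5%.
- **Supported patients outside the exceptions already fail the clause.** A reader might infer that any transfused patient can be called CR. The text does not support that.
- **Later recovery cures many cases.** Best response to day 84 lets a patient with later unsupported recovery be a true CR, and lets a red-cell-dependent patient convert. Section 12.4 states this only for the interim analysis, but the false CRs are in any case limited to patients who never recover unsupported counts within the response window.
- **The infection rate is not the size of the problem.** A reader might take the figures in section 10.1.1, "39.7% and 36.9 of 648 patients respectively", to mean that about 40% of patients could qualify through the infection exception. The 39.7% is an overall infection rate. The relevant event is joint: infection at the time of the qualifying count, a platelet or granulocyte transfusion under that exception, a count lifted over the limit by it, and under 5% blasts.
- **One extra CR at 21 does not decide the trial under K=4.** Both 21/41 (LR 1.5) and 22/41 (LR 3.375) are weak evidence there; the step that crosses is 22 to 23.

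One further reply does not stand. The full IWG criteria may settle these cases, but section 9.2 applies them as summarized in Table 3, and nothing else in the protocol supplies the missing rule.

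**Conclusion.** The point holds in limited form. Both routes follow from the wording of Table 3, and no other section closes them.

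The Treatment Failure route costs 2.4 points of the secondary CR/CRi rate per affected patient at n=41 and removes that patient from the 1-year DFS set. A reader might infer that it also biases the primary endpoint. It would do so only if red-cell-dependent patients ought to be CR, which the documents do not say.

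The supported-count route can add patients to the primary CR count. Its frequency is not in the documents, so the rise in type I error from 4.7% to between 6.2% and 10.0% (K=4: from 3.5% to between 4.7% and 8.3%) is an illustration for an assumed 1 to 3 points. It also assumes that the trial stops whenever 7 or fewer of 17 patients reach CR, whereas the synopsis leaves that to DSMB review. This is a definitional gap of unknown frequency that is cheap to close.

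**What to change.** Change Table 3 for response classification only; transfusion practice is not affected.

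1. Require the neutrophil and platelet counts used for CR to be free of granulocyte or platelet transfusion over a pre-specified interval, whatever the reason for the transfusion. One weekly assessment interval from Table 1, 7 days, is an example.
2. Redefine CRi as under 5% marrow blasts, no blood blasts and no extramedullary disease, with any of neutrophil recovery, platelet recovery or transfusion independence not met. Red-cell dependence, supported counts and both counts low then all have a category. Apply it at the recovery or end-of-treatment marrow; section 5.2.1 already reserves the day-14 marrow for treatment decisions.
3. Derive the class from the recorded product and date of each transfusion.

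The cost is a few lines in Table 3 and a transfusion date on the CRF, with no new procedure. A few CRs will become CRi or be confirmed one CBC later, and a transfusion in the last week before day 57 could cost a CR. CR becomes stricter and CRi wider, so the report should note this when setting the result against the 40% historical rate, whose own CR definition the protocol does not give.

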## 10. SAFETY ASSESSMENTS

### 10.1. Safety Monitoring

#### 10.1.1. Common Adverse Events Attributed to Vosaroxin

The safety profile of vosaroxin is consistent with the common pharmacologic effects of cytotoxic chemotherapeutic agents. Myelosuppression (including associated fatal infections) and gastrointestinal (GI) toxicity (including nausea, diarrhea, and upper GI mucositis) are known risks associated with vosaroxin treatment. Oral mucositis (stomatitis) was the DLT in patients with hematologic malignancies treated with higher doses of vosaroxin: up to 40 mg/m^2 once weekly for 4 weeks (28-day cycle) or up to 90 mg/m^2 once weekly for 3 weeks (28 day cycle; up to 270 mg/m^2/cycle). In patients treated with vosaroxin, oral mucositis is dose limiting and grade 3 or 4 oral mucositis usually appears within 2 weeks after the first dose.

Per the most recent reference safety information (IB, Version 12), infections and febrile neutropenia were reported at a higher frequencies in patients with hematologic malignancies (39.7% and 36.9 of 648 patients respectively) than in patients with solid tumors (12.3% and 9.2% of 284 respectively). The GI toxicities of stomatitis and diarrhea were also reported at higher frequencies in patients with hematologic malignancies (46.8% and 47.7% respectively) than in

patients with solid tumors (11.3% and 17.3% respectively). For patients with hematologic malignancies who received vosaroxin (N = 648), the most common treatment-related AEs (with at least 20% incidence) include nausea (53.2%), diarrhea (47.7%), stomatitis (46.8%), febrile neutropenia (36.9%), decreased appetite (31.3%), vomiting (30.1%), anemia (29.0%), thrombocytopenia (28.5%), neutropenia (20.1%), and fatigue (21.0%). The only two grade 3 and 4 treatment-related AEs reported in at least 20% of all vosaroxin treated patients (N = 932) are febrile neutropenia (26.4%) and neutropenia (21.5%).

For patients with AML treated with higher doses of vosaroxin, oral mucositis is dose limiting and grade 3 or 4 oral mucositis usually appears within 2 weeks after the first dose. Oral mucositis can be managed with standard supportive care (Appendix E). The incidence of combined grade 3 and 4 nausea and vomiting in vosaroxin studies is low (2.7% and 1.4% respectively).

In general, adverse reactions are manageable with standard and diligent supportive care. Myelosuppression and GI toxicities should be managed according to Appendix E within the protocol.

